For the subgroup analysis, the models for the primary outcome variables (Part-O and QoLIBRI) will include the intervention group, all the covariates that define the subgroups, and interactions between each covariate and the intervention group. Test of interactions will reveal if there are subgroups based on a certain covariate (or factor) that respond differently to the RDP or RTP intervention. It is possible that for some covariates, we will not have enough individuals to give information on the outcomes variation in a certain subgroup and that we will not be able to assess the effect for that covariate, while for other covariates, the sample size in each subgroup will be enough to provide information for the data analysis. These numbers cannot be determined a priori. For example, facility discharges are expected to occur in approximately 198 participants (22%) of our sample which will allow adequate sample size for comparison, and males are expected to make up approximately 612 participants and can be compared to females. We may have difficulty comparing race/ethnicity on more specific subgroups such as Asians (expected to be approximately 2% of our participants) and Hawaiian/Pacific Islander (expected to be <1%), but will likely have an adequate sample size to compare Hispanic (11%) to non-Hispanic and Black (17%), White (73%), and other (10%). In this situation, we may have to collapse the categories into a smaller number, such as White, non-Hispanic Black, Hispanic, and Other. Given multiple insurance options across the population as well as across the sites we may not have adequate power to detect differences between every provider, but will explore the effect of relevant subgroups such as private insurance vs. Medicaid vs. Medicare, for example.

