We will explore the effects of the intervention on patient subgroups defined by factors known or hypothesized to have associations with poorer TBI outcome: facility vs. community discharge, race/ethnicity (White, non-Hispanic Black, Hispanic, Other), age (as continuous), male vs. female, lack of or lower degree of caregiver involvement (yes or no), severity of TBI (moderate vs. severe), presence of pre-injury psychosocial limitations (e.g., unemployment, substance abuse, categorized in yes or no) and medical or psychiatric comorbidity (yes or no), as well as study site, resource variability and insurance type (private insurance vs. Medicaid vs. Medicare). These factors will be entered in a single linear regression model in addition to the intervention group, using PART-O-17 as the response variable. Interactions between each factor and the intervention group will be entered in the model and test of interaction will be the test of heterogeneity. Before constructing the model, we will assess whether the explanatory variables (factors) are correlated to each other.

When two or more variables are deemed highly correlated, to avoid problems with collinearity, we will construct the model with the variable that provides the best model (from fit and diagnostic tests).

From previous research, we hypothesize that severity of TBI and presence of pre-injury psychosocial limitations will interact with the intervention group. With our expected sample size, we anticipate being able to address these questions. Some of the factors might not have a statistically significant effect, but have the effect in the expected direction. Effect sizes and confidence intervals will be calculated to express the potential effect of those factors. The results of these analyses will be valuable in designing future studies.

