### **Data Analysis Plan Specific to Each Aim (IR-3, IR-5)**

**General approach:** The expected sample size is very large and we anticipate 100% power to find a difference in PART-O-17, if a difference exists. In addition, the sample size will allow us adequate power to examine our other aims and heterogeneity of treatment effects. We will use a significance level of 0.05 for all the analyses we will perform. Given the large sample size and the extremely high power for the primary outcome, we will not adjust the significance level for multiple comparisons for all the other tests, since it is highly likely that the p-values for those tests will be small. As it is well known and now stated in a publication by the American Statistical Association, the p-value should not be the single deciding measure of the significance of a result. Therefore, we will interpret the results of all non-primary outcomes with caution and will examine effect sizes as well as explicitly report the secondary outcomes status when presenting the results. We will obtain input from our stakeholders regarding the meaningfulness and importance of the effects.

The analysis plan will conform to the intent-to-treat principle: all randomized cases will be included based on their assigned treatment group regardless of actual intervention received. Missing values will be prevented and minimized by implementing the following steps in the manual of operations: 1) Prompt data entry to allow timely detection of any missing data, 2) Procedures for monitoring and tracking data completeness will be in the manual of operations, 3) When missing data are identified, research staff will contact the participant to collect them (if not time-contingent or outside the specified time range for collection). At the end of the study, participants not assessed at the end of intervention will be considered as having missing outcome values.

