#### **Analysis of heterogeneity of treatment effects (HT-1, HT-3, HT-4)**

We will explore the differential effects of the intervention on patient subgroups defined by factors known or hypothesized to have associations with poorer TBI outcome: facility vs. community discharge, minority race/ ethnicity, older age, male gender, lack of or lower degree of caregiver

involvement, greater severity of TBI, presence of pre-injury psychosocial limitations (e.g., unemployment, substance abuse) and medical or psychiatric comorbidity, as well as study site, resource variability and insurance type. These factors will be entered in a single linear regression model in addition to the intervention group, using PART-O-17 as the response variable. Before constructing the model, we will assess whether the explanatory variables are correlated to each other. When two or more variables are deemed highly correlated, to avoid problems with collinearity, we will construct the model with the variable that provides the best model (from fit and diagnostic tests). From previous research, we hypothesize that severity of TBI and presence of pre-injury psychosocial limitations will interact with the intervention group, and those interactions will be included in the model. With our expected sample size we anticipate being able to address these questions.

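### Choosing among correlated moderators by fit to PART-O-17 can drop a true moderator and report its interaction under a correlated factor's name, and the heterogeneity passages disagree on whether the two hypothesised moderators are exempt

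*Combined protocol and SAP*

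**What the plan says.** The heterogeneity plan appears in two places, and three of its statements bear on this point.

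- **Heterogeneity of Treatment Effects (HT-1, HT-2, HT-4, RQ-4), paragraph on the subgroup models.** The models for both primary outcomes contain "all the covariates that define the subgroups, and interactions between each covariate and the intervention group". Nothing is dropped for collinearity.
- **Same section, paragraphs listing the coded factors.** One linear model with PART-O-17 as response is planned: "Interactions between each factor and the intervention group will be entered in the model and test of interaction will be the test of heterogeneity". Before it is built, "we will assess whether the explanatory variables (factors) are correlated to each other". The dropping rule comes next. Its trigger is a judgement of high correlation, made to avoid collinearity, and its instruction is that "we will construct the model with the variable that provides the best model (from fit and diagnostic tests". The next paragraph names two expected moderators: "we hypothesize that severity of TBI and presence of pre-injury psychosocial limitations will interact with the intervention group". It does not say that they are exempt from the dropping rule.
- **Analysis of heterogeneity of treatment effects (HT-1, HT-3, HT-4).** The dropping rule is repeated. The sentence after it names the same two moderators and adds that "those interactions will be included in the model". It does not say whether this overrides the rule, and no other interactions are named.

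Neither place gives a correlation threshold, a fit criterion, an order of priority, or a plan to report the factor left out. On error control, Data Analysis Plan Specific to Each Aim says: "We will use a significance level of 0.05 for all the analyses we will perform".

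**The concern.** A factor's contribution to fit comes mostly from its main effect on PART-O-17. The heterogeneity question is about its interaction with arm, which is a different quantity. The candidate factors were chosen for their links with poorer outcome, so strong main effects are to be expected.

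Suppose A truly modifies the effect of RTP, B does not, and the two are correlated. If B predicts PART-O-17 better, the rule keeps B. B's interaction term then absorbs part of A's interaction and is reported as B's. Two things are at stake. A stated heterogeneity hypothesis may go untested, and a differential benefit may be credited to the wrong patient characteristic. The planned effect sizes and confidence intervals for the surviving factor carry the same misattribution as its p-value.

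**Working it through.** **The plan's own figures.** The power analysis states practically 100% power at effect size 0.5 with 500 patients. With 250 per arm, 0.5 × √(250/2) = 5.59, and Φ(5.59 − 1.96) = 0.9999, so this reproduces. So does the facility-discharge count: 0.22 × 900 = 198. The documents give no power or error rate for any interaction test.

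**Inputs from the documents.** 900 enrolled and 80% retention give 720 analysed. Allocation is 1:1 and the level 0.05; the tests here are two-sided.

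**Assumptions not in the documents.** A (true moderator) has prevalence 40% and B (non-modifier) 35%. Residual SD is 1, and A's interaction with arm is 0.5 SD. The correlation phi is 0.6 or 0.7. Main effects are as in the table. The rule is taken as keeping the factor whose single-factor model has the smaller residual sum of squares.

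**Approximation when A has been dropped.**

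- B's interaction estimates 0.5 × phi × √(0.24/0.2275). At phi 0.6 this is 0.308 SD.
- Its standard error is √(4/(720 × 0.2275)) = 0.156.
- Chance of significance: Φ(0.308/0.156 − 1.96), about 50%. At phi 0.7: 0.359/0.156 = 2.30, about 63%.

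**Approximation with both kept.**

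- A's interaction has standard error √(4/(720 × 0.24 × (1 − phi²))), which is 0.190 at phi 0.6 and 0.213 at phi 0.7.
- Power is about Φ(0.5/0.190 − 1.96) = 75% and Φ(0.5/0.213 − 1.96) = 65%.
- B's test stays at 5%.

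**How often A is dropped.** This turns on A's effect averaged over arms, which is its main effect plus half its interaction, compared with B's main effect. Simulation (1,500 to 3,000 trials per setting, Monte Carlo error about 1 point) gives:

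| Main effects A, B | Interaction against A's main effect | A's averaged effect | phi | A dropped | Power for A: rule / both kept | B significant: rule / both kept |
|---|---|---|---|---|---|---|
| −0.3, −0.6 | offsets | −0.05 | 0.6 | 98% | 2% / 76% | 49% / 6% |
| −0.3, −0.6 | offsets | −0.05 | 0.7 | 98% | 3% / 65% | 60% / 4% |
| −0.4, −0.4 | offsets | −0.15 | 0.7 | 71% | 29% / 63% | 44% / 5% |
| −0.3, −0.6 | reinforces | −0.55 | 0.6–0.7 | 39–47% | 56% / about 75% (phi 0.6) | 19–28% / about 5% |
| −0.4, −0.4 | reinforces | −0.65 | 0.7 | 6% | 85% / 66% | 4% / about 5% |

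A separate simulation with both prevalences at 50% and other main effects agrees on the mechanism. With a 0.4 SD interaction and phi 0.7, B's test rejects in 44–61% of the trials in which A was dropped. If neither factor interacts with arm, the survivor's test rejects in 4.6–5.8%.

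**Smaller interaction.** At 0.3 SD and phi 0.7, with the other settings as in the first row, power for A is 1% under the rule against 30% with both kept. B is declared significant in 27% against 5%.

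**The case against.** **The hypothesised moderators may already be protected.** The analysis section says their interactions will be in the model, and an interaction is hardly interpretable once its factor has been removed. The subgroup-models paragraph says every covariate and interaction is kept. A reader might infer from the coded-factors paragraphs alone that nothing protects severity and psychosocial limitations; the documents do not support that. What stands is that the dropping rule is stated twice without an exemption and no order of precedence is given. The protective sentence also does nothing for the other factors.

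**The large percentages depend on the setting.** In the first two rows A's interaction nearly cancels its main effect, so A loses almost by construction. With the sign reversed the harm shrinks, and in the last row the rule beats keeping both. If A is the more prognostic factor (−0.6 against −0.3, phi 0.6, offsetting), A is dropped in 18% of trials and power is 74% against 75%. This stands. The offsetting sign is still plausible: it describes RTP helping worse-prognosis patients more. The 0.5 SD interaction is also large, close to the 0.533 SD main effect used in the power analysis.

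**The rule may never be triggered.** No correlations are reported. For two factors, 1/(1 − phi²) at 0.6 and 0.7 gives variance inflation of only 1.6 and 2.0. A tempting illustration, facility discharge displacing severity, is limited by arithmetic. With facility discharge at 22% and the other factor at an assumed 40%, the largest possible phi is √(0.22 × 0.60/(0.40 × 0.78)) = 0.65, so the rows at 0.7 cannot describe that pair.

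**B's interaction is not spurious in a marginal sense.** If B travels with A, patients with B do differ in average benefit, which can matter for implementation. This stands too: the fault lies in attribution and in an untested hypothesis. A reader might infer general type I error inflation, but error stays near 5% when there is no heterogeneity.

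**The analysis is exploratory.** The plan promises cautious reading of non-primary results and effect sizes with intervals. That limits the consequence but does not correct the label on the surviving interaction.

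**Conclusion.** The concern holds in a limited form. A rule that selects moderators by outcome fit can drop a true moderator and pass its interaction to a correlate, and the heterogeneity passages give incompatible instructions about what is in the model.

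Harm requires three things together: a pair deemed highly correlated, a real interaction in one member, and a correlate that wins on fit. The documents allow none of these to be quantified, so the tabulated rates are a range over assumptions and not a forecast. The high end needs a more prognostic correlate and an interaction that offsets the moderator's main effect. At the low end the rule does no harm.

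The primary comparison of RTP with RDP is untouched. The change is worth making because the defect lies in a stated rule, not in missing detail, and two moderators were named in advance.

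**What to change.** Reconcile the subgroup-models paragraph, the coded-factors paragraphs and the analysis section so that all three describe one model, including which interactions it contains. Then:

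1. State that TBI severity and pre-injury psychosocial limitations, with their interactions with arm, stay in the model whatever their correlation with other factors or their contribution to fit.
2. For the remaining factors, replace selection by fit and diagnostics with a named measure of association, a threshold, and a written priority order, all fixed before outcome data are seen. A threshold alone is not enough: correlation is symmetric and cannot say which of two factors to omit.
3. Report every omitted factor and the correlation that led to its omission, and describe the retained interaction as not separable from that of the omitted factor.

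If outcome data have already been examined, say so, and report the joint model beside the one-factor-at-a-time interaction models.

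The cost is a few sentences of text and wider intervals where correlated factors are both kept. In the settings above, power for A with both kept falls from about 75% at phi 0.6 to about 65% at phi 0.7. That loss reflects how little the data can separate the two factors.

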### **Study Timeline**

#### *Pre-Enrollment Activities (Months 1-6)*

Startup activities will include hiring personnel, developing a formal study protocol, Institutional Review Board submission and approval, trial registration on Clinicaltrials.gov, and training of all study personnel on study procedures (see Milestones Schedule appendix). TCMs will be trained at a kick-off meeting to coincide with an investigator meeting during a regularly scheduled TBIMS Project Director's meeting. Research staff will be trained via teleconference and via a study dedicated website to increase familiarity with the measures and procedures. Once training of TCMs and RAs is completed, participant recruitment will begin.

#### *Enrollment/Study Protocol Activities (Months 7-48) [RQ-2]*

The methods used to identify and recruit participants, collect data, and minimize attrition and missing data will be drawn from the SOPs and data dictionary developed by the TBIMS National Data and Statistical Center (NDSC) and successfully employed by the TBIMS (see <https://www.tbindsc.org/SOP.aspx>). The success of these procedures is demonstrated by the 80% recruitment rate, 93% retention rate (and 94% retention rate at 1 year by our six sites), and <10% missing data rate of the TBIMS as a whole (while 10% is the missing data benchmark used by the TBIMS, actual missing data rates are considerably lower).

## STUDY METHOD

### **Participants**

#### *Patient Participants*

The target population is composed of inpatients on the rehabilitation unit and their caregivers (if available) who are aged 18 and older and have a diagnosis of moderate-to-severe TBI.

The case definition for TBI will be that used by the TBI Model System (TBIMS): TBI is defined as damage to brain tissue caused by an external mechanical force as evidenced by medically documented loss of consciousness or post-traumatic amnesia (PTA) due to brain trauma or by objective neurological findings that can be reasonably attributed to TBI on physical examination or mental status examination. Potential participants must meet at least one of the following criteria for moderate-to-severe TBI: (1) PTA>24 hours; (2) Trauma related intracranial neuroimaging abnormalities; (3) Loss of consciousness exceeding 30 minutes (unless due to sedation or intoxication); or (4) Glasgow Coma Scale in the emergency department of less than 13 (unless due to intubation, sedation, or intoxication).

#### *Caregiver Participants*

Caregiver participants will be those individuals who will have primary care giving responsibility post rehabilitation care discharge of patients with moderate to severe TBI. Identifying the primary caregiver will be done in consultation and collaboration with rehabilitation care staff, the TBI patient and the TBI patient's involved family and friends. All these sources will be involved in helping us to determine which individual will be most responsible for caregiving following discharge.

### **Identification**

To identify participants, we will review medical records for individuals admitted to inpatient rehabilitation with a primary diagnosis of TBI as defined above. Research study staff will approach patients who meet basic eligibility criteria noted below.

#### *Inclusion Criteria-Patient Participants*

(1) Hospitalized with a moderate-to-severe TBI defined by TBIMS and this study as damage to brain tissue caused by an external mechanical force as evidenced by medically documented loss of consciousness or post-traumatic amnesia (PTA) due to brain trauma or by objective neurological findings that can be reasonably attributed to TBI on physical examination or mental status examination. Potential participants must meet at least one of the following criteria to be considered experiencing a moderate-to-severe TBI:

- (a) PTA>24 hours;
- (b) Trauma related intracranial neuroimaging abnormalities;
- (c) Loss of consciousness exceeding 30 minutes (unless due to sedation or intoxication); or
- (d) Glasgow Coma Scale in the emergency department of less than 13 (unless due to intubation, sedation, or intoxication).

(2) English speaking (we will track non-enrollment due to other language to determine common languages and have consumer dissemination materials translated for more broad use if time and resources permit.);

(3) at least 18 years old;

(4) will be discharged from inpatient rehabilitation to community (private residence, adult home, hotel, homeless) or facility (nursing home, subacute care i.e. skilled nursing facility);

- (5) current admission to inpatient rehabilitation considered their first comprehensive rehabilitation experience, or extension thereof for most recent TBI(e.g. admitted to inpatient rehabilitation, discharged to acute care, then returns to inpatient rehabilitation to complete their initial stay);
- (6) able to provide informed consent, or if unable to provide consent have family or legal guardian to provide informed consent for the patient.

#### *Exclusion Criteria-Patient Participants*

- (1) We will not enroll individuals who are in law enforcement custody at admission to the designated rehabilitation unit or who are taken into custody prior to discharge from the designated rehabilitation unit due to federal restrictions on inclusion of prisoners in research.
- (2) We will not enroll individuals who do not have access to a phone.
- (3) We will not enroll individuals who are unable to complete study procedures due to cognitive/verbal limitations AND do not have a proxy to assist with study procedures.

#### *Inclusion Criteria-Caregiver Participants*

- (1) individuals who will have primary care giving responsibility post rehabilitation care discharge of enrolled patient participants;
- (2) English speaking (we will track non-enrollment due to other language to determine common languages and have consumer dissemination materials translated for more broad use if time and resources permit.);
- (3) at least 18 years old;
- (4) able to provide informed consent.

#### *Exclusion Criteria-Caregiver Participants*

- (1) We will not enroll individuals who are in law enforcement custody due to federal restrictions on inclusion of prisoners in research.
- (2) We will not enroll individuals who do not have access to a phone.

#### **Screening**

As noted above, the screening process involves an initial review of medical records by our research staff for patients with a diagnosis of TBI, or suspected TBI, (see inclusion/exclusion above for further detail) who are being admitted to the inpatient rehabilitation unit at the different study sites. Once a potential participant is confirmed initially eligible based on medical record review, a member of our research team will approach him/her using study talking points to make certain the subject has access to a telephone to participate in the study. The criterion regarding access to a telephone also may be confirmed via observation or via conversation with clinical staff and family members. In addition, certain eligibility criteria may be confirmed or corroborated further via conversation with clinical staff and family members (e.g. discharge destination).

Each site will assign each potential participant identified an ID number unique to that particular site. The patient participant will keep the same ID number if enrolled in the study.

Our research staff members have established communication lines with the clinical staff to ensure patients are approached at appropriate times that do not interfere with clinical care.

